10.2.10. Exploratory Endpoint

CCI

10.2.11. Summary of Analyses

Outcome	Analysis Set	Supports Protocol Objective Number	Subgroups	Statistical Method	Missing Data
Summary of Age at index	All patients	Primary objective	None	Age at index date will be calculated as the difference between index date and date of birth. Summary statistics calculated (as per Section 10.1.1).	Day of birth assumed to be the 15 th of the month. If month is missing, month of birth is assumed to be July, otherwise excluded.
Distribution of sex	All patients	Primary objective	None	Frequency tables and percentages.	Excluded.
Distribution of ECOG performance status at baseline	All patients	Primary objective	None	Frequency tables and percentages. Summary statistics.	Excluded.
Time between ALL diagnosis and initiation of InO (index date)	All patients	Primary objective	None	Frequency tables and percentages. Summary statistics.	Dates will be assumed to be the 15 th of the month. If month is missing, month of birth is assumed to be July, otherwise excluded.
Phase of disease at index date	All patients	Primary objective	None	Frequency tables and percentages.	Excluded.
CD22 expression: percentage of positive cell blasts	All patients	Primary objective	None	Frequency tables and percentages. Summary statistics.	Excluded.
Distribution of ALL cytogenetics	All patients	Primary objective	None	Frequency tables and percentages.	Excluded.
Number of ALL relapses prior to index date	All patients	Primary objective	None	Frequency tables and percentages. Summary statistics.	Excluded.
History of liver diseases prior to index date	All patients	Primary objective	None	Frequency tables and percentages.	Excluded.
Summaries of full blood counts at baseline	All patients	Primary objective	None	Summary statistics.	Excluded.
Summaries of liver function tests at baseline	All patients	Primary objective	None	Summary statistics.	Excluded.
1st line chemotherapy according to national trial or treatment guideline	All patients	Primary objective	None	Frequency tables and percentages.	Excluded.

PFIZER CONFIDENTIAL

Outcome	Analysis Set	Supports Protocol Objective Number	Subgroups	Statistical Method	Missing Data
Summary of number of lines of salvage therapy	All patients	Primary objective	None	Frequency tables and percentages. Summary statistics.	Excluded.
Number of prior HSCTs	All patients	Primary objective	None	Frequency tables and percentages. Summary statistics.	Excluded.
Type of conditioning regimen for each HSCT	All patients	Primary objective	None	Frequency tables and percentages.	Excluded.
Proportion of patients treated with blinatumomab	All patients	Primary objective	None	Frequency tables and percentages.	Excluded.
Number of CAR T-Cell therapies	All patients	Primary objective	None	Frequency tables and percentages. Summary statistics.	Excluded.
Total duration of treatment with InO	All patients	Secondary Objective 1	None	Summary statistics.	Excluded.
Number of cycles of InO, per patient	All patients	Secondary Objective 1	None	Frequency tables and percentages. Summary statistics.	Excluded.
Interrupted cycles of InO	All patients	Secondary Objective 1	None	Frequency tables and percentages. Summary statistics.	Excluded.
Summary of reasons for interruption	All patients	Secondary Objective 1	None	Frequency tables and percentages.	Excluded.
Doses of InO prescribed	All patients	Secondary Objective 1	None	Frequency tables and percentages. Summary statistics.	Excluded.
Modification of doses of InO	All patients	Secondary Objective 1	None	Frequency tables and percentages. Summary statistics.	Excluded.
Summary of reasons for InO modifications	All patients	Secondary Objective 1	None	Frequency tables and percentages.	Excluded.
Proportion of patients treated with Azole antifungal therapy concomitant to InO treatment	All patients	Secondary Objective 1	None	Frequency tables and percentages.	Excluded.
CR, CRi and CR/CRi response rates by the end of InO treatment	All patients	Secondary objective 2	Overall, and by number of salvage therapies in the pre-index	The CR/CRi rate will be estimated as the number and proportion of patients who achieve CR/CRi divided by the total number	Standard imputation for dates (see Section 7). Otherwise excluded.

Outcome	Analysis Set	Supports Protocol Objective Number	Subgroups	Statistical Method	Missing Data
			observation period (0,1, ≥2)	of patients completing treatment with InO (defined as patients with a recorded date of discontinuation of InO). Patients who have not completed treatment with InO will not be included in CR/CRi rate. Kaplan-Meier analysis, time to best response (CR/CRi and CR/CRi) from the start of InO treatment to the end of InO treatment. The median with 95% CI will be calculated.	
Number and proportion of patients achieving MRD negativity	All patients	Secondary Objective 3	Overall, and by number of completed cycles of InO	Frequency tables and percentages. Summary statistics.	Excluded.
Distribution of methods used to assess MRD negativity	All patients	Secondary Objective 3	None	Frequency tables and percentages.	Excluded.
Number and proportion of patients surviving at 3,6 and 12 months after InO initiation	All patients	Secondary Objective 4	Overall, and separately in patients with and without follow-up HSCT	Frequency tables and percentages.	Excluded.
Cause of death	All patients	Secondary Objective 4	Overall, and separately in patients with and without follow-up HSCT	Frequency tables and percentages.	Excluded.
Median OS (95% confidence interval)	All patients	Secondary Objective 4	Overall, and separately in patients with and without follow-up HSCT	Kaplan-Meier analysis, median OS measured as being from the date of InO initiation to the date of death. Patients alive at end of follow-up will be censored at date of last visit.	Standard imputation for dates (see Section 7). Otherwise excluded.
Proportion of patients who are relapse free at 3, 6 and 12 months after InO initiation	All patients	Secondary Objective 5	All patients, separately in patients with follow-up HSCT	Frequency tables and percentages.	Excluded.
Median RFS (95% CI)	All patients	Secondary Objective 5	All patients, separately in patients with	Kaplan-Meier analysis, from InO initiation to date of first relapse or date of	Standard imputation for dates (see Section 7).

PFIZER CONFIDENTIAL

Outcome	Analysis Set	Supports Protocol Objective Number	Subgroups	Statistical Method	Missing Data
			follow-up HSCT	last visit before data collection.	Otherwise excluded.
Median NRM (95% CI)	Patients undergoing follow-up HSCT	Secondary Objective 5	None	Kaplan-Meier analysis, from date of follow-up HSCT to date of death or the date of last visit before date of data collection. 95% CI will also be presented.	Standard imputation for dates (see Section 7). Otherwise excluded.
Proportion of patients initiated on each treatment	All patients	Secondary objective 6	Per treatment (chemotherapy (blinatumomab, other). HSCT, CAR T-cell therapy)	Frequency tables and percentages.	Excluded.
Response to treatment	All patients	Secondary objective 6	Per treatment (chemotherapy (blinatumomab, other). HSCT, CAR T-cell therapy)	Frequency tables and percentages.	Excluded.
Survival following treatment	All patients	Secondary objective 6	Per treatment (chemotherapy (blinatumomab, other). HSCT, CAR T-cell therapy)	Frequency tables and percentages.	Excluded.
Number and proportion of patients experiencing VOD/SOS during the post-index observation period	All patients	Secondary objective 7	All patients, separately in patients with follow-up HSCT, by grade and follow-up treatment (Follow-up chemotherapy after completion of chemotherapy and follow-up HSCT after HSCT)	Frequency tables and percentages.	Excluded.
Treatments received for VOD/SOS	All patients	Secondary Objective 7	All patients, separately in patients with follow-up HSCT	Frequency tables and percentages.	Excluded.
Survival following treatment	All patients	Secondary Objective 7	All patients, separately in patients with follow-up HSCT	Frequency tables and percentages.	Excluded.
Number and proportion of patients experiencing grade 3 or 4 TRAEs	All patients	Secondary Objective 7	All patients, separately in patients with follow-up HSCT	Frequency tables and percentages.	Excluded.

Outcome	Analysis Set	Supports Protocol Objective Number	Subgroups	Statistical Method	Missing Data
Treatments received for grade 3 or 4 TRAE	All patients	Secondary Objective 7	All patients, separately in patients with follow-up HSCT	Frequency tables and percentages.	Excluded.
InO dose delay as a result of grade 3 or 4 TRAE	All patients	Secondary Objective 7	All patients, separately in patients with follow-up HSCT	Frequency tables and percentages.	Excluded.
Number and proportion of patients experiencing other liver dysfunctions	All patients	Secondary Objective 7	All patients, separately in patients with follow-up HSCT	Frequency tables and percentages.	Excluded.
Treatments received for other liver dysfunction	All patients	Secondary Objective 7	All patients, separately in patients with follow-up HSCT	Frequency tables and percentages.	Excluded.
InO dose delay as a result of other liver dysfunction	All patients	Secondary Objective 7	All patients, separately in patients with follow-up HSCT	Frequency tables and percentages.	Excluded.
Peripheral blood blast counts prior to follow-up HSCT	All patients	Secondary Objective 7	All patients, separately in patients with follow-up HSCT	Summary statistics.	Excluded.
Number and proportion of patients with significant risk factors for VOD/SOS	All patients	Secondary Objective 7	All patients, separately in patients with follow-up HSCT	Frequency tables and percentages. Cox regression modelling investigating risk factor association with time to VOD/SOS. Alternatively, logistic regression and odds ratios will be used depending on whether the data is censored.	Excluded.
Overall HSCT rate	Patients who discontinue InO for reasons other than death or lost to follow-up while on InO treatment	Secondary objective 8	None	Frequency tables and percentages.	Excluded.
Rate of patients going directly into HSCT	Patients with follow-up HSCT	Secondary objective 8	None	Frequency tables and percentages.	Excluded.

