Summary measures of: 
 • Total duration of treatment with InO • Number of cycles of InO per patient • Interrupted cycles of InO, including reasons (liver toxicity TRAEs, other AEs, tolerance, treatment failure, and course complete). • Doses of InO prescribed • Modification of doses of InO, including reasons (liver toxicity TRAEs, other AEs, tolerance, treatment failure, and course complete). • Azole antifungal therapy concomitant to InO treatment 	Dates are DD/MM/YYYY unless specified 
 • InO treatment: start date and end date of each cycle, cycle completed / interrupted (if interrupted provide reason for discontinuation) • Azole antifungal therapy including fluconazole, voriconazole, itraconazole and posaconazole (and other indicated in the medical records): date started, date end.
Secondary objective: To summarise CR/CRI rates following initiation of InO, overall and according to the number of salvage therapies received prior to InO initiation.	

Summary measures of:
 
 • CR, CRi and CR/CRi response rates by the end of InO treatment, overall and according to the number of salvage therapies in the pre-index observation period (0, 1, ≥ 2). • Median time to CR/CRi (95% CI) 	
Dates are DD/MM/YYYY unless specified
 
 • Date of start and stop of InO treatment (stop date is date of discontinuation) • Response to InO treatment first recorded after end of treatment: date, response (CR, CRi, stage disease, progression) • Number of salvage therapies for ALL prior to index date.

Secondary objective: To summarise MRD negativity rates following initiation of InO, and describe the number of cycles of InO needed to attain MRD negativity.
	

 • Number and proportion of patients achieving MRD negativity overall and by the number of completed cycles of InO (after 1, 2, ≥ 3 cycles of InO) in patients evaluated by flow-cytometry/ molecular assessment / both. 	
Dates are DD/MM/YYYY unless specified
 
 • Date of InO initiation • Start and stop date of each cycle of InO • Date of discontinuation of InO • MRD negativity recorded: Y/N. If Y test performed (flow cytometry, molecular assessment, both), result: negative / positive, date of test.

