9.7. Data analysis

[figure not shown]
Detailed methodology for summary and statistical analyses of data collected in this study will be documented in a separate statistical analysis plan (SAP), which will be dated, filed and maintained by the sponsor. The SAP may modify the plans outlined in the protocol; any major modifications of primary endpoint definitions or their analyses would be reflected in a protocol amendment.

Analyses will be performed by pH Associates using Stata (StataCorp LLC) and R statistical software (version 3.4.1 or later). Data from all participating centres will be pooled for analysis.

Descriptive statistics (number, percentages, means, standard deviations, medians, quartiles, minimum, maximum, number of missing and non-missing values), as appropriate to the data collected, will be used to describe baseline demographic and clinical characteristics for the overall study. Treatment patterns, treatment outcomes and TRAEs will also be reported using descriptive characteristics. Frequency and percentages will be used to describe categorical variables. All percentages will be reported to the nearest whole number; therefore, in reporting study results in tables, figures and associated text, percentages may not add up to 100% due to rounding. Means, standard deviations, medians, quartiles, minimum, and maximum, will be used to describe continuous variables. Patients who are still alive and have not progressed at the last visit date without clinical evidence of progression will be censored. Kaplan-Meier plots will be used to describe data related to OS, RFS and time to CR/CRi. A summary table of the number of events and censored patients at each monthly interval will also be included.

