9.9. Limitations of the research methods

- Several sources of selection bias may be introduced in the study:
 - Patients treated as part of the CUP may differ from patients treated via private purchase and patients treated via NHS commissioning.
 - Patients were recruited from larger centres enrolled in the CUP, which may differ from smaller centres in terms of demographic and clinical characteristics, and therefore may not be representative of all real-world patients treated with InO.
- Patients may be lost to follow-up due to the occurrence of AEs, lack of efficacy or other reasons. The use of Kaplan-Meier curves to obtain estimates of median OS, RFS and time to CR/Cri takes into account patients' attrition.
- The interpretation of data collected retrospectively will be dependent on the completeness and quality of the medical records and the reliability of the abstraction of data from the medical records. However, SDV will be employed to identify and correct abstraction errors.

- This is a descriptive study and no analyses to control for confounding will be carried out; therefore, no definitive causal relationships between InO and study endpoints can be made.
- The overall sample size of the study is relatively small, and therefore CR/CRI rates and MRD negativity rates may be estimated with relative imprecision, and 95% CIs may be relatively wide. In addition, the small sample size may not allow the conduct of univariate and multivariate Cox modelling to estimate the risk of VOD/SOS in patients with follow-up HSCT.

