3.1.1. Key Definitions

- *Index date: the date of initiation of the first cycle of InO.*

[figure not shown]
- *Baseline period: period from 6 months prior to index date. The closest observation recorded during the baseline period to the index date will be used as baseline data (when more than one observation is available).*
- *Pre-index observation period: period from the date of ALL diagnosis to the index date.*
- *Post-index observation period: period from the index date until the date of death, or date of latest visit at the time of data collection, whichever is soonest.*
- *CR/CRi rate: number of patients who achieve CR/CRi divided by the total number of patients completing treatment with InO (defined as patients with a recorded date of discontinuation of InO).*
- *MRD negativity rate: proportion of patients in whom MRD-negative status is observed, among patients in whom MRD negativity status has been assessed, at any time until the end of treatment with InO (defined as the date of recorded discontinuation of InO).*
- *OS: time from index date to death.*
- *RFS (interchangeable with EFS for the purpose of this SAP): time from index date to the earliest date of the following events: death, progressive disease (including objective progression, relapse from CR/CRi, treatment discontinuation due to global deterioration of health status) and start of new induction therapy or posttherapy HSCT without achieving CR/CRi.*
- *NRM: Time from the date of follow-up HSCT until death without disease progression or relapse. Deaths from any cause without prior progression are events. Events related to the disease such as relapse, progression are competing events, loss of follow-up are censored.*

Patients will be observed from the start of the pre-index observation period until the end of the post-index observation period. For the purpose of identifying risk factors for VOD/SOS and replicating the findings by Kantarjian et al¹ follow-up will be defined as the post-index observation period, and patients will be censored at the date of the last recorded clinic visit prior to data collection.

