Total duration of treatment with InO will be summarised as a quantitative variable (see [Section 10.1.1](#)); measures of central tendency (mean and median) and dispersion (standard deviation, interquartile range [IQR] and range) and the number of non-missing and missing values will be calculated. The number of cycles of InO per patient, the number of interrupted cycles of InO, doses of InO prescribed and the modification of doses of InO will be summarised as ordinal variables (see [Section 10.1.3](#)). Reasons for interruption and modification of InO cycles andazole antifungal therapies concomitant to InO treatment will be summarised as categorical variables (see [Section 10.1.2](#)). The proportion of patients who temporarily or permanently stopped InO treatment due to an AE will be presented as proportions and percentages.

10.2.3. Secondary Objective 2

To summarise CR/CRi rates following initiation of InO, overall and according to the number of salvage therapies received prior to InO initiation.

The CR/CRi rate will be estimated as the proportion of patients who achieve CR/CRi divided by the total number of patients completing treatment with InO (defined as patients with a recorded date of discontinuation of InO). Patients who have not completed treatment with InO or do not have a recorded discontinuation date will not be included. Patient response to treatment will be presented as a binary variable (see [Section 10.1.4](#)). Response rates will be presented overall and by number of salvage therapies in the pre-index observation period (0,1, ≥ 2). Kaplan-Meier analysis will be utilised to analyse time to CR/CRi and the median time to CR/CRi, as well as 95% CI, will be calculated using the Kaplan-Meier method and presented as per [Section 10.1.5](#).

10.2.4. Secondary Objective 3

To summarise MRD negativity rates following initiation of InO and describe the number of cycles of InO needed to attain MRD negativity.

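### Kaplan-Meier for time to CR/CRi names no competing event, so the curve can exceed the observed response proportion and show a median when fewer than half of patients responded

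*SAP*

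**What the plan says.** The CR/CRi row of SAP 10.2.11 gives the estimator and the window: "Kaplan-Meier analysis, time to best response (CR/CRi and CR/CRi) from the start of InO treatment to the end of InO treatment". It continues: "The median with 95% CI will be calculated". SAP 10.2.3 says the same in its text: "Kaplan-Meier analysis will be utilised to analyse time to CR/CRi and the median time to CR/CRi". Protocol 9.7 plans the plot: "Kaplan-Meier plots will be used to describe data related to OS, RFS and time to CR/CRi". The protocol abstract also names Kaplan-Meier for this median.

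On censoring, protocol 9.7 has one general rule: "Patients who are still alive and have not progressed at the last visit date without clinical evidence of progression will be censored". Neither document says what happens, for this endpoint, to a patient who dies, progresses or stops InO without CR/CRi.

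Competing events are defined only for NRM (SAP 3.1.1): "Events related to the disease such as relapse, progression are competing events".

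Protocol 9.9 acknowledges attrition: "Patients may be lost to follow-up due to the occurrence of AEs, lack of efficacy or other reasons". It then says that Kaplan-Meier estimates of median OS, RFS and time to CR/CRi take this attrition into account.

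The CR/CRi rate is a separate estimator. It is a crude proportion among patients with a recorded InO discontinuation date (protocol 9.7, SAP 10.2.3).

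**The concern.** Kaplan-Meier censoring assumes that a patient who leaves the risk set has the same future chance of the event as those who remain. That is not credible here. Table 1 in protocol 9.3 summarises "Interrupted cycles of InO, including reasons (liver toxicity TRAEs, other AEs, tolerance, treatment failure, and course complete"), so leaving treatment can itself reflect failure or toxicity. A patient who dies, or who moves to another therapy without remission, can no longer contribute a response to InO. These are competing events. They are not ordinary loss to follow-up, and Kaplan-Meier does not handle them in the way protocol 9.9 claims.

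Two things are at stake. The plotted curve may rise above the CR/CRi proportion reported beside it. The table may also print a median time to CR/CRi when fewer than half of the patients ever reached CR/CRi, so that no cohort median exists.

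**Working it through.** The documents give no figure for time to CR/CRi, so there is none to reproduce. The check compares two estimators on assumed data.

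**Inputs from the documents:** about 25 patients (protocol 9.5); cycles of 3 to 4 weeks (protocol 7); a CR rate of 80.7% with InO in the phase III trial (protocol 7).

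**Assumptions:** all response and stopping times, because the documents give none. Non-responders are censored when InO stops. Responses are counted before stops at the same time point.

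**Formulas.** Kaplan-Meier response is 1 − Π(1 − dⱼ/nⱼ), where dⱼ is responders and nⱼ is patients at risk at time j. Cumulative incidence with stopping as a competing event and no other censoring equals cumulative responders divided by N.

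**Example 1, 12 of 25 respond.** Cycle 1: 8 respond, 9 stop. Cycle 2: 4 respond, 4 stop.
- At risk in cycle 2: 25 − 8 − 9 = 8.
- Kaplan-Meier: survival is 17/25 = 0.68, then 0.68 × 4/8 = 0.34. Response is 66%, with the median in cycle 2.
- Cumulative incidence: 8/25 = 32%, then 12/25 = 48%. The median is not reached.

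**Example 2, 18 of 25 respond.** Cycle 1: 12 respond, 3 stop. Cycle 2: 5 and 3. Cycle 3: 1 and 1.
- Kaplan-Meier: 13/25 = 0.52; × 5/10 = 0.26; × 1/2 = 0.13. Response is 87%, with the median in cycle 2.
- Cumulative incidence: 48%, 68%, 72%. The median is also in cycle 2.

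**Example 3, 20 of 25 respond.** Day 21: 14 respond, 3 stop. Day 49: 6 respond, 2 stop.
- Kaplan-Meier: 1 − (11/25)(2/8) = 89%. Crude: 80%. The median is day 21 both ways.

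**Example 4, 11 of 25 respond, no early stopping.** Day 21: 6 respond. Day 49: 5 respond, then 14 stop.
- Kaplan-Meier: 1 − (19/25)(14/19) = 44%. Crude: 44%. There is no median either way, and no bias.

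**Simulation** (n = 25, 4,000 data sets per setting; response times 60/30/10% at days 21, 49 and 77):

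| Stopping of non-responders at days 21/49/77 | True response | Mean excess of Kaplan-Meier over crude | Kaplan-Meier median present, among data sets with under half responding |
|---|---|---|---|
| 50/35/15% | 30% | 18 points | 41% |
| 50/35/15% | 40% | 21 points | 65% |
| 50/35/15% | 50% | 21 points | 82% |
| 50/35/15% | 80.7% | 13 points | hardly any such data sets |
| 20/40/40% | 40% | 7 points | 29% |
| 20/40/40% | 50% | 8 points | 51% |
| 20/40/40% | 80.7% | 7 points | hardly any such data sets |

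At 80.7% response the two medians differ in under 1% of data sets under either stopping pattern.

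**The case against.** The strongest objection is that the censoring of non-responders is inferred. The SAP gives an estimator and a window but no rule, and the missing-data entry in the same row excludes what cannot be imputed. This stands: a reader might infer that the plan prescribes such censoring, and it does not. Censoring is nevertheless what the stated window and estimator naturally produce. If non-responders were dropped instead, the median would describe responders only and would exist at any response rate without being labelled so. The text needs correcting under either reading.

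A reader might also infer that the study's response rate is overstated. It is not. The CR/CRi rate is computed separately as a crude proportion, and nothing says that the height of the Kaplan-Meier curve will be reported as a rate.

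The only InO response rate in the documents is 80.7%, where the median hardly changes. The figure of under 50% in protocol 7 is for relapsed/refractory ALL generally. This limits the practical effect. Disagreement with the crude proportion is also not certain, as Example 4 shows.

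A reader might infer that medians will be printed within the salvage-therapy strata. The subgroup table in SAP 7.3 and the text of 10.2.3 attach those strata to the response rates. Only the merged row in 10.2.11 could be read as stratifying the median.

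Table 1 in protocol 9.3 collects the response first recorded after treatment ends. Counting discontinuation itself as an immediate competing event would therefore turn patients whose CR/CRi is documented just after the last dose into failures. This objection is right, and it shapes the fix.

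Finally, the monthly tables of events and censored patients and the swimmer plots (SAP 10.1.5) would let a careful reader see the problem. They do not correct the median.

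**Conclusion.** The point holds for the Kaplan-Meier curve and its median, and for nothing else. As written, the plan allows a curve above the observed CR/CRi proportion and a median when fewer than half responded. In the assumed 12-of-25 example the gap is 66% against 48%. Across the simulated settings tabulated above, the mean excess is 7 to 21 points.

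The size depends on assumed response and stopping times and on the inferred censoring. Bias arises only if some non-responder leaves before a later response. A false median is a real risk when response is near or below half, and close to none near 80%, although the curve still sits too high there.

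This is a descriptive secondary summary with no hypothesis attached. It should be corrected before analysis, but it does not threaten the study's main results.

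**What to change.** In SAP 10.2.3 and the CR/CRi row of 10.2.11, replace Kaplan-Meier for this endpoint with an Aalen-Johansen cumulative incidence of CR/CRi from index date:

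- **Competing events:** death; progression; start of other anti-leukaemia therapy or HSCT without CR/CRi; and InO discontinuation with no CR/CRi at the first response assessment after the end of treatment. The last wording keeps responses first documented after the last dose as responses.
- **Censoring:** only patients without response who are still on InO, or awaiting that assessment, at cut-off.
- **Population:** state it. If it is all treated patients, note that it differs from the denominator of the CR/CRi rate, so the two need not agree exactly.
- **Reporting:** give a median only if cumulative incidence reaches 50%. Add median (IQR) time to CR/CRi, labelled as among responders only.

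Align the abstract and section 9.7 of the protocol, and remove time to CR/CRi from the statement in protocol 9.9 that Kaplan-Meier accounts for attrition.

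The cost is wording and slightly more analysis work. Dates of response, InO discontinuation, progression, later therapy, HSCT and death are already collected (protocol 9.3 and Annex 2), and the planned Stata and R have standard routines. Protocol 9.7 lets the SAP modify the protocol's analysis plans and calls for an amendment only for major changes to primary endpoints; this endpoint is secondary. The curve will look less favourable than the Kaplan-Meier version.
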